### **Study Procedures**

## Outcome measures

Aim 1: Feasibility will be determined by achievement of the following:

- a. Recruitment of 40 children with hemiplegia in 24 data collection visits at study sites (average 2/visit: 3 sites, 2 visits/month, 4 months);
- <5% of participants reporting adverse effects (dizziness or motion sickness) during or within 15 minutes post HMD-VR use; and
- c. 90% of participants able to complete the whole protocol in the available clinic timeframe.

**Aim 2:** *2.a.Paper-and-pencil test:* Total score from the Beery-Buktenica VMI test 6th Edition Short form. *2.b. Touchscreen computer and HMD-VR:* Eye-hand proximity, defined as the lag between eye end time and hand end time (i.e. eye movement time – hand movement time), is a gold-standard measure of visual-motor integration that quantifies the coordination of eye and hand movements.

**Aim 3:** Total movement time during the visual-motor integration object transport task in HMD-VR with and without the complex environment.

**Secondary outcomes**. Multiple other temporal and spatial variables related to eye, head and hand movements will be collected for hypothesis-generating purposes. These include reaction time, movement time, amplitude (eye and hand), touch and transport accuracy (hand), peak velocity, sub-movements and trajectory straightness (hand), and spatial position and pitch, yaw and roll orientations.

Data management and analysis: We will follow established procedures for eve tracking and kinematic data processing to discard trials in which artifacts are present or children are looking elsewhere and to determine head and hand movement start and end times. RStudio will be used for data analyses. We will check assumptions of normality for parametric analyses; if un-met, non-parametric equivalent tests will be undertaken. Aim 1: Feasibility outcomes will be recorded with counts and proportions. Aim 2: We will calculate the median of the 5 trials for each hand and target location. Of primary interest are estimates of variability as inputs needed for sample size calculations for the subsequent study. Recognizing lack of power, we will undertake inferential statistics for hypothesis generating purposes, including a multiple correlation using Pearson's t-test for each hand and target location. Aim 3: Paired t-tests per hand. Hypothesis-generating analyses for secondary outcomes will compare performance estimates within individuals (touch screen vs HMD-VR, dominant vs non-dominant hand) and between individuals (CP vs typically developing), accounting for age, lesion, and HMD-VR experience. Equipment related: 1) Sanitization: We use Cleanbox VR technology to disinfect VR headsets using UVC light. All peripherals will be sanitized with alcohol wipes and left to dry for a minimum of 15 minutes between users. 2) Transport/set up: Potential difficulties transporting and setting up equipment in different settings can be mitigated by diligent equipment protection. We have transported equipment many times for other studies at the Boston Children's Museum. HMD-VR tracking accuracy is not affected by differing ambient light levels. Study related: 1) Reliability of VMI scoring: The PI (a pediatric physical therapist) will train for VMI scoring by using the VMI manual, attending a web-based presentation on scoring, and scoring practice tests. 2) Lack of experience with eye-tracking processing/analyses: We will consult with [name], Assistant Professor in the College of Science at Northeastern and eye-tracking expert, who will advise on analyses. [name] was unable to be a named investigator on this grant due to budget restrictions. 3) Recruitment: Previous recruitment at Boston Children's Hospital CP clinic (unfortunately not a site for this study due to lack of space for clinic VR assessments) yields 2-3 eligible participants/week for identical inclusion criteria. Estimates from other sites are between 3-10 eligible children per clinic. 4) Time for in-clinic assessment: Recognizing the many demands on children and families' time in a busy clinic

environment, we will endeavor to approach families at their arrival and leverage positive relationships with clinic staff to determine the optimal testing time.

Participant related: 1) Previous experience with VR: This may impact performance; this information will be collected in the demographic questionnaire and included as a covariate in the analyses. 2) Potential impact of HMD weight on head or reaching movements: There are no studies of impact of HMD weight on children's movements; the short duration of our testing should mitigate any issue. 3) Left vs right-sided lesion differences in spatial abilities: We will include hemispheric lesion side as a covariate in the analyses, but this is complicated by the fact that many children with unilateral impairments have bilateral lesions. Any hemispheric-specific differences will inform the next study. 4) Intra- and inter-individual variability in this population: Children with hemiplegia are a heterogeneous population and their performance varies across repeated tests within individuals and between children. We will take this into account by basing sample size calculations for subsequent work on effect sizes from this study.

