# **RESEARCH METHODS/PLANS**

Design: Cross-sectional, repeated-measures design.

*Participants:* We will recruit children aged between 7 and 16 years old with a diagnosis of hemiplegia (due to CP or stroke) at Gross Motor Function Classification System (GMFCS) Levels I-III and Manual Ability Classification System (MACS) Levels I-II. We will also recruit a comparison group of age and gender-matched typically developing peers. Inclusion criteria include the ability to read and write English. Children need to be able to see, hear and respond to auditory and visual cues. As such, exclusion criteria are a greater than 10-degree elbow or shoulder flexion contracture in the affected arm, uncorrected visual deficits (e.g., homonymous hemianopsia, oculomotor disturbance, or cortical visual impairment), uncontrolled photosensitive seizures (occurrence of at least one seizure in the last 3 months), hemineglect or cognitive impairments that would prohibit participation (as judged by a parent).

**Recruitment and sites:** The research assistant (RA) will consult the child's electronic medical records and the clinic MD to determine eligibility. They will approach eligible children and families and provide an overview of the study. Children and caregivers will complete informed assent and consent. Recruitment and data collection will take place at Maine Medical Center Pediatric CP clinic (Portland, ME), Spaulding Salem Outpatient Center for Children CP clinic (Salem, MA), and Massachusetts General Hospital Pediatric Stroke clinic (Boston, MA). In addition, we will email the families of the 62 children with CP or stroke in our lab database to invite them to participate in the lab. Typically developing children recruited via emails from our database will also be tested in the ReGame-VR Lab.

**Sample size and power**: We will recruit a convenience sample of 40 children with hemiplegia and 40 typically developing children. This pilot study is designed to obtain estimates of within- and between-child variability for effect size calculations to power a subsequent, more rigorous study design.

*Institutional Research Board Approval:* IRB approval will be obtained from Northeastern University, facilitating a shared and expedited agreement with IRBs of participating sites.

[figure not shown]

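### Do the Aim 1 feasibility criteria need rewriting because they do not say whether lab recruits count toward the 40 children, or which group the <5% adverse-effect limit covers?

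*Combined protocol and SAP*

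**What the plan says.** Outcome measures, Aim 1, opens with "Feasibility will be determined by achievement of the following" and lists three criteria:

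- Recruitment: "Recruitment of 40 children with hemiplegia in 24 data collection visits at study sites (average 2/visit: 3 sites, 2 visits/month, 4 months").
- Tolerability: "<5% of participants reporting adverse effects (dizziness or motion sickness) during or within 15 minutes post HMD-VR use".
- Completion: "90% of participants able to complete the whole protocol in the available clinic timeframe".

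Elsewhere, Sample size and power states "We will recruit a convenience sample of 40 children with hemiplegia and 40 typically developing children". The Participants paragraph adds the comparison group: "We will also recruit a comparison group of age and gender-matched typically developing peers". Recruitment and sites names three hospital clinics and then, as an addition, describes emailing the families of the "62 children with CP or stroke in our lab database to invite them to participate in the lab". The typically developing children are also tested in the lab.

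For analysis, the Data management and analysis section says only "Feasibility outcomes will be recorded with counts and proportions". It gives no denominator and no rule for assigning lab recruits.

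**The concern.** Two things look wrong on a first reading.

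**Recruitment.** The criterion ties its 40 children to clinic visits at three sites. The whole hemiplegia sample is also 40, and a second route through the lab feeds the same group. If enrolment closed at 40 in total, one child recruited through the lab would leave at most 39 from the clinics. The criterion would then fail however well the clinics recruited. If lab children were instead counted toward it, it could pass when the clinics fell short. The stated rate of 2 per visit also does not multiply out to 40.

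**Tolerability.** The recruitment criterion names children with hemiplegia; this one says only participants, a word that the protocol uses for both groups. The same data can pass on one denominator and fail on the other, and the choice could be made after the results are known. Pooling could also dilute events in the patient group.

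The completion criterion leaves its group unnamed too, but its reference to clinic time already points to children tested in clinic. That is a matter of wording only.

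At stake is whether the feasibility verdict, the study's first aim, can be interpreted.

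**Working it through.** **1. The plan's own figure.** Inputs from Outcome measures: 3 sites, 2 visits a month, 4 months. Visits = 3 × 2 × 4 = 24, as stated. Rate needed = 40 / 24 = 1.67 per visit, which rounds to the stated average of 2. Taken exactly, 2 per visit would give 24 × 2 = 48. The target of 40 in 24 visits is unambiguous, so this is rounding.

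**2. Does the lab route block the recruitment criterion?** Let L be the number of lab recruits with hemiplegia. The documents give no figure for L.

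| L (assumed) | Clinic children if the total is capped at 40 (40 − L) | Total if clinics supply 40 and the lab is extra (40 + L) |
|---|---|---|
| 0 | 40 | 40 |
| 1 | 39 | 41 |
| 5 | 35 | 45 |
| 10 | 30 | 50 |

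The criterion is blocked only in the middle column, with L of 1 or more. That column needs a rule closing enrolment at 40, and the plan has none: 40 is given as a convenience sample to be recruited. Introducing the lab route as an addition fits the right-hand column equally well.

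If a cap did exist and each of the 62 families independently supplied a recruit with probability p, the chance of no lab recruit would be (1 − p)^62. That is 54%, 29%, 4% and 0.15% for p = 1%, 2%, 5% and 10%. These values of p are assumed. The 62 are children with CP or stroke, and the plan does not say how many have hemiplegia or meet the age and function criteria. The figures are illustrative and depend on the unstated cap.

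**3. Can the clinics supply 40 alone?** The recruitment paragraph in the analysis section expects 3–10 eligible children per clinic.

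- Read per visit: 24 × 3 = 72 to 24 × 10 = 240 eligible. Uptake needed is 40/72 = 56% down to 40/240 = 17%.
- Read as a total per site: 3 × 3 = 9 to 3 × 10 = 30 eligible, fewer than 40.

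The first reading makes the target attainable. On the second, the clinics could not reach 40 and the lab would be needed to fill the sample. Restricting the lab route is therefore not clearly harmless.

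**4. How far does the tolerability denominator matter?** The limit is strictly below 5%.

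- n = 40: 1/40 = 2.5% passes, 2/40 = 5.0% fails. At most 1 event.
- n = 80: 3/80 = 3.75% passes, 4/80 = 5.0% fails. At most 3 events.

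Let h and t be events in the hemiplegia and typically developing groups, independent Binomial(40, p) with the same assumed p. The hemiplegia-only reading passes if h ≤ 1; the pooled reading passes if h + t ≤ 3.

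| Assumed p | Pass, n = 40 | Pass, n = 80 | Verdicts differ |
|---|---|---|---|
| 2% | 81% | 92% | 15% |
| 3% | 66% | 78% | 22% |
| 5% | 40% | 43% | 24% |
| 8% | 16% | 11% | 13% |
| 10% | 8% | 3.5% | 7% |

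At 5%, 13% of studies fail on 40 and pass on 80, and 11% do the reverse. Pooling is therefore not uniformly lenient.

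**5. What does the verdict carry?** Neither reading measures the rate precisely: the exact 95% interval for 1/40 is 0.06% to 13.2%. A pass would not establish a true rate below 5%, nor would 2/40 rule one out. Counts reported by group let any reader apply either denominator.

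**The case for a change.** The best case for a change is that the plan says feasibility is determined by meeting these thresholds, and a pass/fail rule needs a defined count and denominator whatever the power. The text supports two readings of each of the first two criteria, the readings can give different verdicts, and a sentence written before enrolment is cheap, whereas a choice made after the data are seen is less credible.

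Much of this stands. The counting rule and the denominator are unwritten, and the disagreement rates above are not trivial. What does not stand is the step from there to a necessary amendment.

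- The claim that the recruitment criterion cannot be met rests on an enrolment cap that the plan does not contain.
- Holding lab invitations until after the 24 visits would trade speed and sample size for a cleaner count; enrolling lab children on top means recruiting more. Both are recruitment choices rather than corrections.
- Restricting the 5% limit to the hemiplegia group is one of two defensible choices. The change of term between the criteria, from children with hemiplegia to participants, leans toward everyone who wore the headset. A fixed limit of 1 child in 40 would also be wrong if lab children were added: 2/41 = 4.88% is below 5%.
- Exact intervals are good practice but would not settle who is counted.

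**Conclusion.** The concern identifies a gap that analysts can fill sensibly, and no change to the plan follows. The recruitment result can be reported as children recruited at the three clinics over the 24 visits, with lab recruits shown separately. Adverse effects can be reported for each group as counts over those who used the headset. Completion can be reported for children tested in clinic. Those summaries already fit the planned counts and proportions, and they make both readings visible.

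The largest effect found is a 24% chance that the two tolerability readings disagree, at an assumed common rate of 5%; across assumed rates of 2% to 10% the range is 7% to 24%. It affects a descriptive label in an unpowered pilot whose stated purpose is to estimate variability for a later study, and no decision to proceed depends on it.

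This conclusion assumes that results are reported by group and by recruitment route, and that no enrolment stop at 40 operates outside the documents. If the authors revise the text for other reasons, stating who counts toward the 40 and naming the tolerability denominator as a proportion would be a helpful clarification.

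### Could lab-tested children turn a clinic failure into a pass on the third feasibility criterion of Aim 1?

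*Combined protocol and SAP*

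**What the plan says.** The plan sets three thresholds under Outcome measures, Aim 1: "Feasibility will be determined by achievement of the following". The first names both group and setting: "Recruitment of 40 children with hemiplegia in 24 data collection visits at study sites". The second concerns tolerability and is worded for participants in general: "<5% of participants reporting adverse effects (dizziness or motion sickness". The third is the one at issue: "90% of participants able to complete the whole protocol in the available clinic timeframe". The list joins them with 'and', so feasibility needs all three.

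The Participants paragraph covers both study groups. After the children with hemiplegia it adds: "We will also recruit a comparison group of age and gender-matched typically developing peers". Sample size and power gives the numbers: "We will recruit a convenience sample of 40 children with hemiplegia and 40 typically developing children". Recruitment and sites names three hospital clinics, then says of children with hemiplegia already known to the lab: "we will email the families of the 62 children with CP or stroke in our lab database to invite them to participate in the lab". Of the peers it says: "Typically developing children recruited via emails from our database will also be tested in the ReGame-VR Lab". No other setting is given for the peers.

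For analysis, Data management and analysis says only that Aim 1 is reported as counts and proportions. It defines no analysis set for the third criterion.

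**The concern.** The first criterion specifies its group and setting; the third switches to a word that elsewhere in the protocol covers both groups. Up to half the planned sample, and possibly some children with hemiplegia, are tested where no clinic schedule presses on them. Their completion says nothing about whether the protocol fits into a clinic visit, which the plan itself lists as a study risk.

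If those children were counted, easy completions in the lab could mask poor completion in clinic, and the third criterion could be declared met when fewer than 90% of clinic children finished. Two related gaps point the same way. The plan does not say whether database recruits fall within the 40 children with hemiplegia or come on top of them. It also does not say that the tolerability proportion will be shown by group.

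**Working it through.** **Inputs from the documents.** 40 children with hemiplegia and 40 peers (Sample size and power); a 90% threshold and a limit of less than 5% (Outcome measures, Aim 1); peers and database recruits tested in the lab (Recruitment and sites).

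**Assumptions.** The documents give neither completion rates nor the expected number of database recruits, so both are varied below.

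**The plan's own figures.** The 90% is a chosen threshold, so there is nothing to reproduce. The visit count in the first criterion does reproduce: 3 sites × 2 visits × 4 months = 24.

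**What each reading of the third criterion requires.** The pass count is 0.9 × N, rounded up.

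1. *Clinic-tested children only:* 36/40 with no database recruits in the lab; 27/30 if 10 of the 40 are tested there.
2. *All 80 in the denominator, but only completion within a clinic limit counts as success:* lab children cannot succeed, so the ceiling with no database recruits is 40/80 = 50%. The criterion could never be met, so this cannot be intended.
3. *All 80 in the denominator, with lab completion credited as success:* 72/80 needed. If every peer completes, 72 − 40 = 32 clinic completers suffice, and 32/40 = 80%.

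Only the third reading produces the false pass.

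**How likely a false pass would be.** Take a true clinic completion of 80% and no database recruits. Clinic-only scoring passes with probability P(X ≥ 36), where X is Binomial(40, 0.8). Pooled scoring passes with probability P(X + Y ≥ 72), where Y is Binomial(40, q) and q is completion among peers.

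| Scoring | Chance of passing |
|---|---|
| Clinic only | 0.076 |
| Pooled, q = 1.00 | 0.593 |
| Pooled, q = 0.95 | 0.312 |
| Pooled, q = 0.90 | 0.132 |
| Pooled, q = 0.80 | 0.013 |

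The inflation shrinks quickly as q falls. When the two settings complete equally at 80%, pooling gives fewer false passes than clinic-only scoring.

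**Database recruits within the 40.** With 10 of them, the pooled chance is 0.871, 0.518, 0.210 or 0.013 (all lab children at 100, 95, 90 or 80%), against 0.123 for 27/30 in clinic. If enrolment stops at 40, however, even one lab recruit leaves at most 39 at the study sites. The first criterion then fails as worded, and so does overall feasibility, whatever the third shows.

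**Database recruits on top of the 40.** With 10 extra, the total is 90 and 81 completers are needed. If all 50 lab children complete, 81 − 50 = 31 clinic completers suffice, and 31/40 = 77.5%. The first criterion does not block this case, but it still depends on the third reading and on every lab child finishing.

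**Tolerability.** Less than 5% of 80 allows at most 3 children: 3/80 = 3.75%, while 4/80 = 5% fails. If all three had hemiplegia, that group would stand at 3/40 = 7.5%. The criterion concerns symptoms during or shortly after headset use, so all children exposed to the headset are its natural denominator. A split by group would be descriptive.

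**The case for a change.** The strongest argument for a change is that the clinic phrase describes the time limit and not who is counted. Even a reader who leaves out the peers must still decide about database recruits with hemiplegia. With 10 of these among the 40, 24/30 = 80% in clinic becomes 34/40 = 85% across all hemiplegia and 74/80 = 92.5% across everyone. A threshold that decides feasibility is better settled before results are known. Settling it would take a sentence and no new data, and higher completion in a quiet lab than in a busy clinic is plausible.

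Part of this stands: the visible text does not state the denominator, and the arithmetic is correct. It does not show that the plan is wrong. A time limit that exists only in clinic tells the analyst whom the criterion can apply to, and this disposes of database recruits as well as peers.

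Clinic-only wording is also not free of difficulty. Restricting the criterion to children actually tested in clinic could drop those who consented but were never tested for lack of time, and they are the failures it should catch. A smaller denominator is also noisier: at a true 80%, the chance of a false pass is 0.076 with 40 clinic children, 0.123 with 30 and 0.206 with 20.

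**Conclusion.** The concern does not call for a change. The denominator of the third criterion is unstated, not wrongly stated, and its wording points to clinic-tested children. A sensible analyst would score those children, count any who consented in clinic but ran out of time as non-completers, and report lab completion separately. Group and test setting are known for every child, so this can be tabulated without amending anything.

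The worst case without database recruits is a pass at 80% clinic completion (32/40), and it needs both the less natural reading and all 40 peers finishing. Ten recruits on top of the 40 would lower that to 77.5% on the same conditions. Even then the first two criteria must also be met. The study is a convenience-sample pilot whose feasibility results are reported as counts and proportions, and no inferential result depends on this choice.

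The remaining points are also matters of detail. The first criterion already counts recruitment at study sites, and tolerability by group is a reporting preference. The conclusion rests on the visible text; an opening part of the document was not available and may define the Aim 1 population. All completion rates and recruit numbers used here are assumptions.

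### Aim 2 eye-hand proximity is named as an end-time lag, but the bracketed formula gives a different quantity unless movement time runs from a common cue

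*Combined protocol and SAP*

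**What the plan says.** All references are to the combined protocol and SAP.

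- **Outcome measures, Aim 2 (2.b).** Eye-hand proximity, for both the touchscreen and the headset, is "defined as the lag between eye end time and hand end time (i.e. eye movement time – hand movement time". Two references are cited for the measure.
- **Outcome measures, Secondary outcomes.** Reaction time and movement time are listed as separate variables: "These include reaction time, movement time, amplitude (eye and hand". Neither term is defined.
- **Participants.** Cues are mentioned, but not as a time origin: "Children need to be able to see, hear and respond to auditory and visual cues".
- **Data management and analysis.** Processing is intended "to determine head and hand movement start and end times"; eye times are not named in that phrase. For Aim 2, "We will calculate the median of the 5 trials for each hand and target location". The purpose is then given: "Of primary interest are estimates of variability as inputs needed for sample size calculations for the subsequent study".
- **Sample size and power.** "This pilot study is designed to obtain estimates of within- and between-child variability for effect size calculations".
- **Participant related, item 4.** Heterogeneity is to be handled by "basing sample size calculations for subsequent work on effect sizes from this study".

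**The concern.** The outcome sentence gives a verbal definition (a difference of end times) and then, as an equivalent, a formula (a difference of movement times). Movement time in the usual sense is a duration, from the start of a movement to its end. A difference of durations is blind to which effector started first; a difference of end times is not. Listing reaction time separately supports the duration reading, because a movement time counted from the cue would already contain the reaction time.

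An analyst who codes the words and one who codes the bracket could therefore produce different outcome variables from the same recordings. A constant onset lag would shift only the mean. If the onset lag varies between trials, children, hands or devices, the variances and correlations also change. Those variances are what the pilot is meant to hand on to the next study.

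**Working it through.** The plan states no figure for this measure, so there is nothing to reproduce. The check is an identity, followed by illustrations with assumed inputs.

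**1. Identity.** Let Es, Ee be eye onset and end, and Hs, He be hand onset and end.

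- Named lag: A = Ee − He
- Bracketed formula, movement time from onset to end: B = (Ee − Es) − (He − Hs)
- Onset lag: O = Es − Hs
- Hence B = A − O.

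A and B coincide only if O = 0. If both movement times are instead counted from a common cue at time 0, the bracket becomes Ee − He and equals A exactly.

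**2. One trial (assumed times, ms).** Cue at 0, eye 200 to 400, hand ending at 1000.

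| Hand onset | A = 400 − 1000 | O = 200 − Hs | B = 200 − (1000 − Hs) |
|---|---|---|---|
| 200 | −600 | 0 | −600 |
| 350 | −600 | −150 | −450 |
| 500 | −600 | −300 | −300 |

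The end lag is the same in all three rows; the bracketed value halves between the first and the last.

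**3. Effect on variance (assumed k and r).** Let k = SD(O)/SD(A) and r = corr(A, O). Then

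- Var(B)/Var(A) = 1 + k² − 2rk
- corr(A, B) = (1 − rk)/√(1 + k² − 2rk), which is smallest at r = k, where it equals √(1 − k²).

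| k | r = −0.5 | r = 0 | r = 0.5 | Smallest corr(A, B) |
|---|---|---|---|---|
| 0 | 1.00 | 1.00 | 1.00 | 1 |
| 0.1 | 1.11 | 1.01 | 0.91 | √0.99 = 0.995 |
| 0.25 | 1.31 | 1.06 | 0.81 | √0.9375 = 0.968 |
| 0.5 | 1.75 | 1.25 | 0.75 | √0.75 = 0.866 |

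A simulation of 1,000,000 draws agreed: 0.811 at k = 0.25, r = 0.5, and 1.750 at k = 0.5, r = −0.5. For a fixed difference in milliseconds, required sample size is proportional to variance, so these ratios would carry straight into the next study's n.

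**4. A second set of assumptions.** Take hand movement-time SD 150 ms, eye movement-time SD 10 ms, SD of the hand's delay behind the eye 50 to 150 ms, and correlation of that delay with hand movement time −0.5 to 0.5. Var(B) = 150² + 10² = 22,600.

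- Delay SD 50, correlation −0.5: Var(A) = 22,600 + 2,500 − 7,500 = 17,600; Var(A)/Var(B) = 0.78.
- Delay SD 150, correlation 0.5: Var(A) = 22,600 + 22,500 + 22,500 = 67,600; Var(A)/Var(B) = 2.99 (simulation: 2.98).

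On the scale of step 3 these are 1/0.78 = 1.28 and 1/2.99 = 0.33. The lower end falls below the table because this case implies r = (22,500 + 11,250)/(150 × 260) = 0.87, outside the ±0.5 used there. The spread shows how far the answer depends on the inputs.

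**5. Order of median and subtraction (assumed ms).** Five trials with B = −640, −600, −700, −660, −620 and O = −200, −350, −180, −150, −300. Adding the medians gives −640 + (−200) = −840. Taking A = B + O in each trial gives −840, −950, −880, −810, −920, with median −880. The named lag therefore cannot in general be recovered from summary medians; it has to be formed per trial.

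**The case against.** The strongest reply is that this is an undefined term, not a proven contradiction. An end time needs a zero point, and if the bracketed times share it the equivalence is exact. The verbal definition comes first and an analyst following it would compute the right thing. The two cited references, the established processing procedures that the plan invokes, or the eye-tracking expert who is to advise could each settle the zero point. An opening section and a figure are also not available for review. The consequence is not shown from the trial's own data, and the pilot's inference is declared hypothesis-generating.

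Much of this stands. The common-cue reading is not excluded, the size is unknown, and the variance tables reflect chosen inputs. Forming the lag per trial is also the natural reading of the median instruction, so that part of the fix only makes it explicit.

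The wording problem remains. No available text says that movement time runs from a cue, and the separate listing of reaction time points the other way. Expert advice or general procedures do not cancel a formula written into the outcome definition. The plan itself lists limited experience with eye-tracking analysis as a study risk, which is a reason not to rely on unstated convention.

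**Conclusion.** The concern holds: the definition is wrong as written, and the point is minor. On the better-supported reading of movement time, the bracketed formula differs from the named end-time lag by exactly the onset lag. Confidence is high for that wording conflict, on the text available, and does not extend to any effect on results.

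Size and direction cannot be found from the documents. If the onset lag is small or steady, variances and correlations are almost untouched (variance ratio 0.91 to 1.11 at k = 0.1 for r within ±0.5). If it varies appreciably, the variability estimate passed to the next study could be materially too large or too small for the measure named. Both versions can be computed from the same recordings, so nothing is lost if this is settled before processing.

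**What to change.** Before any trial data are processed:

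1. In Outcome measures, Aim 2 (2.b), define eye-hand proximity as eye end time minus hand end time on one synchronised clock, computed in each trial before the five-trial median is taken.
2. Delete the bracketed formula, or state that both of its times run from a common cue.
3. For consistency of wording only, add eye to the head and hand start and end times named in Data management and analysis.

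The cost is one sentence and one word. No new data are needed: Materials and tasks describes eye and hand recording on both set-ups, and eye and hand timing variables are already among the secondary outcomes.
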